8.3 REPORTING OF SERIOUS ADVERSE EVENTS AND UNANTICIPATED PROBLEMS 29

8.3.1 *Sponsor-Investigator reporting: notifying the Mayo IRB* 29

8.3.2 *Sponsor-Investigator reporting: Notifying the FDA*..... 30

8.4 STOPPING RULES..... 31

8.5 MEDICAL MONITORING 31

8.5.1 *Internal Data and Safety Monitoring* 31

9 DATA HANDLING AND RECORD KEEPING..... 31

9.1 CONFIDENTIALITY 31

9.2 SOURCE DOCUMENTS 31

9.3 CASE REPORT FORMS 32

9.4 RECORDS RETENTION 33

10 STUDY MONITORING, AUDITING, AND INSPECTING 33

10.1 STUDY MONITORING PLAN 33

10.2 AUDITING AND INSPECTING 33

11 ETHICAL CONSIDERATIONS 34

12 STUDY FINANCES 34

12.1 FUNDING SOURCE 34

12.2 SUBJECT STIPENDS OR PAYMENTS 34

13 PUBLICATION PLAN 34

14 REFERENCES 35

LIST OF ABBREVIATIONS

AE	Adverse Event/Adverse Experience
BCR	Biochemically recurrence
CFR	Code of Federal Regulations
CRF	Case Report Form
CT	Computerized Tomography
DSMB	Data and Safety Monitoring Board
eGFR	estimated Glomerular Filtration Rate
FDA	Food and Drug Administration
FDG	Fluorodeoxyglucose
GCP	Good Clinical Practice
HIPAA	Health Insurance Portability and Accountability Act
IB	Investigator's Brochure
IND	Investigational New Drug Application
IRB	Institutional Review Board
mpMRI	Multiparametric magnetic resonance imaging
PCa	Prostate cancer
PET/CT	Positron Emission Tomography/Computerized Tomography
PET/MR	Positron Emission Tomography/Magnetic Resonance
PHI	Protected Health Information
PI	Principal Investigator
PSA	Prostate specific antigen
SAE	Serious Adverse Event/Serious Adverse Experience
SOP	Standard Operating Procedure
T	Tesla

Study Summary

Title	Staging of Untreated Patients with Very High-risk and High-risk Prostate Carcinoma Utilizing Hybrid C11-choline PET/MR and Pelvic Multiparametric MRI for Personalized Precise Treatment: a Pilot Study
Running Title	C11-choline PETMR and pelvic mpMRI on primary prostate cancer
Protocol Number	16-007897
Phase	NA
Methodology	Prospective, pilot study
Overall Study Duration	16 weeks
Subject Participation Duration	90 minutes, single day, in the nuclear medicine suite.
Single or Multi-Site	Single
Objectives	1): Test whether a hybrid combination of focused C-11 choline PET/MR and pelvic mpMRI on a PET/MR system is feasible. 2): Determine the efficacy (added values) of a hybrid combination of molecular focused C-11 choline PET/MR and functional and anatomic pelvic mpMRI in comparison with clinical findings. 3): Determine the efficacy (added values) of a torso C-11 choline PET/MR in comparison with conventional CT and bone scan in depicting metastasis to lymph node and bone.
Number of Subjects	20
Diagnosis and Main Inclusion Criteria	Clinically diagnosed high and very high risk prostate cancer. Adult patients who are able to provide informed consent.
Study Product, Dose, Route, Regimen	C-11 choline PET tracer, One dose, totally 12-14 mCi, intravenous administration while patient is lying on the table
Duration of Administration	1 study day
Reference therapy	None
Statistical Methodology	Descriptive statistics will be used, including sensitivity, specificity, and accuracy, based on histopathological correlation.

1 Introduction

This document is a protocol for a human research study. This study will be carried out in accordance with the applicable United States government regulations and Mayo Clinic research policies and procedures.

1.1 Background

Prostate cancer is the most common solid cancer in men in the United States and the second most common cancer death in American men¹. Early and correct diagnosis of prostate cancer together with accurate staging is vital for appropriate clinical management strategy. To date, morphological and functional pelvic mpMRI and molecular imaging C11-choline PET have been playing vital roles in standard of care of prostate cancer.

Pelvic mpMRI, typically including T1-weighted, T2-weighted, diffusion-weighted imaging (DWI) and dynamic contrast-enhanced imaging (DCEI) with or without MR spectroscopic imaging (MRSI), is an established imaging modality and has been increasingly utilized for lesion detection and characterization, monitoring for active surveillance, detection of local recurrence in suspect cases, and MR guided intervention. In a prospective study of 70 consecutive patients with histopathologic correlation, the sensitivity, specificity, false-positive and false-negative rates, and the accuracy of mpMRI for extracapsular extension and seminal vesicle invasion have been reported to be 78.2% and 80%, 80.9% and 97%, 19.1% and 3.7%, 21.7% and 20%, 80% and 95.7%, respectively². However, the major limitation of pelvic mpMRI is the distant metastasis outside the field of view of prostate cancer.

Choline, a component of the phosphatidylcholines increased in prostate cancer, can be radiolabelled with either 11Carbon (C11-choline) and 18Fluoro (F11-choline). Unlike F18-fludeoxyglucose (FDG) tumoral uptake, which depends on increased cellular glycolytic pathway activity, choline uptake depends on active cell membrane synthesis, a metabolic pathway which more reliably reflects tumor metabolism in prostate cancer. C-11 choline PET has been shown to help identify sites of metastatic disease in men with biochemical recurrence after primary treatment failure. In the past decade, multiple investigations have demonstrated satisfactory sensitivity and specificity for the detection of recurrent PCa patients, and led to the FDA approval of C-11 choline production at Mayo Clinic 2012³⁻⁵.

Additional effort has been taken to compare pelvic mpMRI and C11-choline PET in BCR PCa patients and demonstrated complimentary role of them for restaging prostatectomy patients with suspected recurrent disease. Kitajima K and colleagues compared the C11-choline PETCT with pelvic mpMRI with endorectal coil in detection of local recurrence, pelvic nodal metastasis and distant metastasis. They found that mpMRI is superior to C11-choline in detection of local recurrence; PET is superior for pelvic lymph node metastasis⁶.

The newly FDA approved hybrid GE SIGNA 3T PET/MR scanner provides an opportunity to investigate the clinical value of combined C11-PET/MR and pelvic mpMRI in primary prostate cancer. It is anticipated that the improved comprehensive imaging techniques may more

accurately stage untreated patients with high risk prostate cancer as well as better characterize the intra-parenchymal tumor. Therefore, we wish to determine the feasibility and efficacy (added value) of a hybrid, combined torso and focused C-11 choline PET/MR with pelvic mpMRI in characterizing and staging very high-risk and high-risk prostate cancer patients, which could provide a more accurate tumor characterization and staging information and lead to individualized precise treatment.

1.2 Investigational Agent

The investigational agent for this study is C11-choline, a cyclotron synthesized PET tracer to be manufactured in the Mayo Clinic Arizona radiochemistry facility.

1.3 Clinical Data to Date

Since 2000, there have been several studies investigating clinical role of choline PET and PETCT in diagnosing and staging primary prostate cancer. However, there is limited sensitivity and specificity in differentiating primary prostate cancer from normal prostate tissue due to overlapping choline uptake by hyperplastic prostate tissue, high-grade intraprostatic epithelial neoplasia (HGPN), prostatitis, BPH, even urinary excreted activity in the base of urinary bladder and urethra. In addition, there is no proven significant correlation between C11-choline uptake by localized primary prostate cancer and serum PSA level, Gleason score^{7,8}. Therefore, there is clinical consensus of limited clinical value of choline PET and PETCT in characterizing primary PCa.

However, the pursuit of combined advantages of choline PET and pelvic mpMRI in PCa persists. In one recent clinical trial, it is found that fused F18-Choline PET/MR images could provide added value for MR guided transrectal prostate biopsies⁹.

1.4 Dose Rationale

The dose of C-11 choline selected for use in the study patients is 12-14 mCi,(444-518 MBq) based on prior published reports^{6, 10, 11}. The tracer must be given intravenously.

1.5 Risks and Benefits

C-11 choline is involved in phosphorylation process integrated into phospholipids in the cell membrane as part of phosphatidylcholine, which is vital in prostate cancer cell. The main risk involves the exposure to the radioactivity associated with the C-11 isotope incorporation. This exposure has been calculated to be much lower than the F-18 FDG. In addition, there is no radiation risk related to MR scan. For MR safety concern, each subject will undergo MR safety screening performed by PET/MR technologist prior to imaging.

2 Study Objectives

Primary Objective:

- 1) Test whether a hybrid combination of focused C-11 choline PET/MR and pelvic mpMRI on a PET/MR system is feasible

Secondary Objective(s):

- 1) Determine the efficacy (added values) of a hybrid combination of molecular focused C-11 choline PET/MR and functional and anatomic pelvic mpMRI in comparison with clinical findings.
- 2) Determine the efficacy (added values) of a torso C-11 choline PET/MR in comparison with conventional CT and bone scan in depicting metastasis to lymph node and bone.

3 Study Design

This study will be a prospective study to test and optimize the feasibility of hybrid 3T PET/MR scan in diagnosing and staging high and very high risk prostate cancer patients.

The FDA approved C-11 choline PET tracer at a dose of 12-14 mCi will be administered intravenously prior to fused PET/MR scan, and prior to diagnostic pelvic mpMRI scan while patient lying in the scanner.

In addition, single dose of Gadavist® (Gadobutrol, Bayer) is at no more than 0.1 mmol/kg will be administered intravenously for pelvic mpMRI.

The whole imaging procedure will be conducted on an FDA approved GE SIGNA 3T PET/MR scanner.

The C11-choline PET/MR and pelvic mpMRI findings and results will be compared with serum PSA level, Gleason score, clinical CT and nuclear medicine whole body bone scintigraphy findings, and histopathological results obtained through standard of care management.

Our primary interest is to investigate the feasibility of hybrid C11-Choline PET/MR fusion and pelvic mpMRI in imaging primary prostate cancer.

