3.4 Primary Study Endpoints

Patient: Completion of all imaging examinations with laboratory results.

Data analysis:

Objective 1: Descriptive study. With biopsy and/or surgical histopathology as gold standard, the sensitivity, specificity and accuracy of PET/MR will be calculated.

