7.1 Sample Size Determination

Our null hypothesis is the hybrid C11-choline PET/MR and pelvic multiparametric MRI will have an equal accuracy of detecting patients with malignant lymph nodes in the very high risk/high risk prostate cancer patients compared to that in the conventional CT and bone scan method. With 20 patients, a McNemar's test with a 0.05 two-sided significance level will have 82% power to reject the null hypothesis if the difference in accuracy of the two methods is 0.3 or greater and assume discordant pairs is expected to be 0.31.

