7.2 Statistical Methods

Descriptive Statistics

Descriptive statistics will be used to describe the average time of the total procedure, patients' tolerance and satisfaction level about the procedure. Paired t-test will be used to compare the suspicious lymph nodes and suspicious osseous lesions in the pelvis and extrapelvic regions detected by hybrid C11-choline PET/MR and pelvic multiparametric MRI method and by conventional CT and bone scan to investigate if the new method is able to detect more lymph nodes and osseous lesions compared to the conventional method. Paired t-test will also be used to compare the average SUV of lymph nodes and osseous lesions in the pelvis and extrapelvic regions by new method with that by conventional method to investigate if the new method provided more clarity in terms detecting the lymph nodes and lesions compared to the old method. If the patients' biopsy and surgery results available, sensitivity, specificity, positive predictive value and negative predictive value of detecting malignant lymph nodes and osseous lesions by the new method and by conventional method will be estimated and compared using McNemar's test.

Handling of Missing Data

As the sample size is 20 and imaging is completed over one day, no missing imaging data is anticipated.

Multiplicity

In current project, there is one primary objective and we don't have to adjust for multiple comparison.

Interim Analysis

There will not be interim analysis for the study.

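### Feasibility is the primary objective, but replacing non-finishers and analysing completers only makes completion 100% by construction, and no criterion for feasibility is stated

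*Combined protocol and SAP*

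**What the plan says.** Section 2 gives one primary objective: "Test whether a hybrid combination of focused C-11 choline PET/MR and pelvic mpMRI on a PET/MR system is feasible". Section 3 repeats the emphasis: "Our primary interest is to investigate the feasibility of hybrid C11-Choline PET/MR fusion and pelvic mpMRI in imaging primary prostate cancer".

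Section 3.4 sets the endpoint as "Patient: Completion of all imaging examinations with laboratory results". It then gives the analysis: "Objective 1: Descriptive study. With biopsy and/or surgical histopathology as gold standard, the sensitivity, specificity and accuracy of PET/MR will be calculated". Completion is thus the patient-level endpoint, but the statistics named for Objective 1 are diagnostic accuracy measures. Section 7.2 adds that "Descriptive statistics will be used to describe the average time of the total procedure, patients' tolerance and satisfaction level about the procedure". None of these carries a target or cut-off.

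The only hypothesis is in section 7.1 and concerns something else: "Our null hypothesis is the hybrid C11-choline PET/MR and pelvic multiparametric MRI will have an equal accuracy of detecting patients with malignant lymph nodes".

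Three further provisions decide who is counted:
- Section 3.2: twenty subjects are to complete, and more candidates may be screened to reach that number.
- Section 4.4: a subject who cannot finish the PET/MR because of claustrophobia, or who afterwards declines the standard evaluation and imaging, is withdrawn. Early withdrawals are replaced, to hold a target stated there as 10.
- Section 7.3: the only analysis population is subjects who completed every study procedure and follow-up.

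**The concern.** A feasibility question is answered by the subjects who do not get through the session. Here those subjects leave the study, are replaced, and are excluded from the only analysis population. A study in which everyone finished and one in which half of the starters gave up would produce the same analysed data on completion.

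No criterion elsewhere fills the gap. The alpha, effect size and sample size in 7.1 belong to a nodal accuracy comparison and say nothing about how many sessions must be completed. If the report then concludes that the session is feasible, that conclusion could not have come out otherwise under the plan as written.

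**Working it through.** **1. The plan's own figure.** Section 7.1 states 82% power for McNemar's test with n = 20, two-sided alpha 0.05, difference d = 0.30 and discordant proportion ψ = 0.31. Miettinen's approximation is

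power = Φ{[d√(nψ) − z·ψ] / √[ψ² − d²(3 + ψ)/4]}

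= Φ{[0.30 × √6.2 − 1.96 × 0.31] / √[0.0961 − 0.0745]} = Φ(0.1394 / 0.1471) = Φ(0.948) = 82.8%.

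This agrees with the stated figure under that approximation. All its inputs concern accuracy, so it supplies no feasibility criterion.

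**2. What the current rules produce.** Enrolment continues until C = 20 complete, and the analysis set is those C subjects. Completion in that set is C/C = 20/20 = 100% for any number of starters S. Among starters it is 20/S:

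| Starters S (assumed) | Completion among starters | Exact 95% CI | Completion in the 7.3 population |
|---|---|---|---|
| 20 | 100% | 83.2–100% | 100% |
| 22 | 90.9% | 70.8–98.9% | 100% |
| 25 | 80.0% | 59.3–93.2% | 100% |
| 40 | 50.0% | 33.8–66.2% | 100% |

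The values of S are illustrations, because the documents give no expected completion rate. The intervals are Clopper-Pearson and treat S as fixed. Under enrolment until twenty complete S is random, which is one reason to define the feasibility set as the first 20 starters.

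**3. What a mark would do once starters are the denominator.** Let X be completions among the first 20 starters, X ~ Binomial(20, p), with P(X ≥ k) = Σ C(20, x) pˣ(1 − p)²⁰⁻ˣ over x = k to 20. The rates p = 70% (unacceptable) and p = 95% (good) are assumptions.

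| Mark k | P(X ≥ k) at p = 70% | P(X ≥ k) at p = 95% |
|---|---|---|
| 14 | 60.8% | 100% |
| 16 | 23.8% | 99.7% |
| 18 | 3.5% | 92.5% |
| 20 | 0.1% | 35.8% |

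For k = 18, the one-sided error rises to 9.1% if the unacceptable rate is 75%, and power falls to 67.7% if true completion is 90%. The exact 95% CI at 18/20 is 68.3–98.8%.

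**4. Dependence on N.** With no failures the lower exact 95% limit is 0.025^(1/N). This is 69.2% for 10/10 and 83.2% for 20/20. The conflict between 10 in section 4.4 and 20 in the Study Summary, 3.2, 7.1 and 7.2 therefore changes what any mark means.

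**The case against.** The strongest reply is that this is a pilot and says so. The title calls it one, the Study Summary gives the methodology as descriptive, and 3.4 labels Objective 1 a descriptive study. The verb in the objective is loose, since section 3 also speaks of investigating and optimizing feasibility, and no follow-on decision is tied to the answer. That stands. A reader might infer that a formal test or pass mark is obligatory, and the documents do not support that. They do support the need for a completion proportion with an informative denominator, because describing feasibility requires one and the plan does not provide it.

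Second, high completion is expected: 4.2 excludes patients who cannot tolerate MRI, and 7.2 anticipates no missing imaging data. This also stands. The 70% rate above is an assumed floor, not a forecast. A reader might also infer that results such as 14/20 could be called feasible under the present plan. They cannot arise in the 7.3 population, so the figures in step 3 apply only after the denominator is changed.

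Third, a reader might infer that the gap cannot be repaired at analysis. That goes too far. Section 4.4.2 keeps data collected up to withdrawal, so if starters are logged, completion with a CI can still be reported descriptively. What cannot be recovered later is a mark chosen before the count is known.

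Finally, the 75–80 minutes in section 3.3 might be read as a time criterion. It is a planned duration, not a limit.

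**Conclusion.** The concern holds in this form: the primary question is feasibility, no criterion for it is stated, and the replacement rule combined with the completers-only population fixes observed completion at 100%. No planned result would count against feasibility. That conclusion comes from reading 3.2, 4.4 and 7.3 together and needs no assumed rate. The size of what could be hidden does depend on assumptions: between 22 and 40 starters, true completion would be 91% down to 50% with an identical analysis set. Safety follow-up and image collection are not affected. The fault lies in the denominator and the missing criterion, and adding a mark to the existing population would not cure it, because the mark would be met automatically.

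**What to change.** Amend 3.4, 7.2 and 7.3 together, before the first scan if possible:

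1. **Population (7.3).** Add a feasibility set of all subjects who start the session. Count withdrawn or replaced subjects as non-completions. Replacement may continue for the accuracy analyses.
2. **Estimate (3.4, 7.2).** Report the number starting, the number completing and the proportion with an exact 95% CI.
3. **Criterion (3.4, 7.2).** State in advance the count or lower confidence bound at which the session will be called feasible. One example is at least 18 of the first 20 starters, with exact one-sided alpha 0.035 at an assumed 70% and power 92.5% at an assumed 95%. The sponsor may choose other rates. The form of the rule must be explicit, because the two forms differ: at 18/20 the lower limit of the two-sided 95% CI is 68.3%, below 70%, while at 19/20 it is 75.1%.
4. **If no mark is set.** Report the proportion and CI descriptively, with no feasible or not-feasible verdict.
5. **Sample size (4.4).** Reconcile the target of 10 with 20 elsewhere before fixing the mark.
6. **Session time.** Describe it against the expected 75–80 minutes in 3.3, labelled as a planned duration.

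The cost is a few sentences in a minor amendment and a log of starters, with no additional scans or readers. The downside is that the study can then formally miss its primary objective.

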3.1 General Description

It is possible that improved comprehensive imaging techniques may more accurately stage untreated patients with high risk prostate cancer as well as better characterize the intra-parenchymal tumor. It is of interest to focus on potential synergy between molecular focused C-11 choline PET and functional and anatomic pelvic mpMRI. Therefore, we wish to determine the feasibility and efficacy (added value) of a hybrid, combination of torso and focused C-11 choline PET/MR with pelvic mpMRI on a clinical 3T PET/MR system in characterizing and staging very high-risk and high-risk prostate cancer patients, which could provide a more accurate tumor characterization and staging information and lead to individualized precise treatment.

3.2 Number of Subjects:

A total of twenty subjects will complete the study. Additional candidates may be screened to ensure completion of twenty subjects.

3.3 Duration of Participation

Subjects will complete one day of in-department participation. A second study day will consist of a phone call to the subject after completion of day 1.

Human subjects will be subject to Mayo Department of Radiology policies and procedures. Candidates for enrollment will be first queried by the study coordinator for possible exclusion using the departmental MRI safety guidelines for clinical MRI. The study coordinator will review the medical history and use the subject's serum creatinine level to determine his eGFR based on patient age, gender, and ethnicity. If necessary, the subject will undergo a blood test to determine an up-to-date creatinine level, performed at no expense to the subject. eGFR will be determined prior to performing any contrast-enhanced scan.

Patient flow in the nuclear suite

Treated naïve patients with high risk or very high risk prostate cancer (NCCN risk stratification), who require clinical imaging evaluation including 1) pelvic mpMRI, 2) abdominopelvic CT, 3) bone scan, and 4) other imaging studies as clinically indicated.

Informed consent

C-11 choline PET/MR on GE Signa PET/MR System at 3 Tesla at one session (70-80 minutes)

Part 1: C-11 choline torso (multi-station) PET/MR with C-11 choline injection

Part 2: Hybrid (simultaneous acquisition) dedicated focused pelvic PET/MR pelvic multiparametric MRI without and with gadolinium MR contrast.

IMAGING TECHNIQUES**PET/MR scanner/equipment**

Clinical GE SIGNA 3 Tesla PET/MR system

PET/MRI Technique (Figure 1)

1. There are two integrated components of fused PET/MR and focused Pelvic mpMRI
 - a. Indications/Protocols: Primary prostate cancer.

Part	Description of imaging sequences
1	Torso (multi-station) PET/MR fusion scan with injection dose of C-11 choline
2	Hybrid focused (single-station) PET/MR and mpMRI of the pelvis (simultaneous acquisition of pelvic PET/MR and mpMRI without and with IV gadolinium contrast at the same table position)

- Parts 1 and 2 will be done at one session with the patient on the same PET/MR table.
- .
- The entire PET/MR fusion with focused pelvic mpMRI scanning time is 75-80 minutes.

Part 1: Torso PET/MR Fusion Scan with C-11 choline

- Coil: Three pieces of array coils from vertex of head to the level of upper thigh; No use of endorectal coil.
- Patient supine, head first
- Arms down for all procedures
- Metallic objects should be removed from the patient whenever possible

PET Tracer:

While patient lying on scanner table, 444-518MBq (12-14ⁱ mCi) C-11 choline will be injected as a bolus through a catheter inserted into a large peripheral vein.

Scan Range:

- Routinely from upper thigh to vertex of head, otherwise specified

Scan direction for PET

- Inferior to superior
- Start imaging immediately after the injection of tracer and acquire images with 2–5 minutes per bed position (totally about 5-6 bed positions). The total scanning duration is around 25-30 minutes

MR attenuation correction:

- Simultaneous PET/MR imaging with PET emission data reconstructed in 3D time-of-flight mode at multiple bed positions. During each bed position, coronal Dixon fat/water sequence, in-phase, and out-phase images will be performed for MR segmented attenuation correction.
- Diagnostic quality axial LAVA-FLEX only was obtained simultaneously with PET emission imaging acquisition at each bed position.

Part 2: Hybrid Focused PET/MR and mpMRI of the Pelvis (simultaneous acquisition of pelvic PET/MR and mpMRI without and with IV gadolinium contrast)

MR contrast agent and medicine

- For a contrast-enhanced scan the technologist will load and connect a power injector for administration of contrast material via a peripheral venous access. The contrast material and dose are both determined by the radiologist subject to departmental policy.
- Typically a single dose of Gadavist® (gadobutrol, Bayer) is used for studies of the prostate gland at our institution. The target contrast dose is no more than 0.1 mmol/kg for subjects with eGFR of higher than 30 mL/minute/1.73 m². Those with a GFR of 30 or less will not be admissible to the study. Contrast material is administered at 3 ml/sec followed by a saline flush of 20 ml at 3 ml /sec.
- 1 mg of glucagon will be administered subcutaneously at the start of the scan as an anti-peristaltic. Glucagon will not be given if the patient has a history of DM.

The following multiparametric prostate MR protocol will be applied. Simultaneous PET emission image will also be acquired. The total mpMRI scan time is around 40-50 minutes.

- Multiparametric MRI of the pelvis technique utilizing an institutional clinical MRI protocol.

Sites	Image sequences
Pelvis	
	Axial T1-weighted LAVA-FLEX*
	Axial DWI
Prostate (high resolution with small FOV)	
	Sagittal T2 FRFSE
	Axial T2 FRFSE
	Axial FOCUS DWI
	Coronal T2 FRFSE
	Axial DCE
Pelvis	
	Post Gd ax LAVA-FLEX (water only, fat only)

* Axial T1-weighted LAVA-FLEX acquired in Part1. may be used for pre-contrast T1-weighted images.

Image review:

- PET/MR fusion study, including PET emission data, MRAC image and focused pelvis PET/MR fusion images will be sent to MIM Vista workstation for review by an independent, experienced board certified nuclear medicine radiologist without knowing clinical findings except for high risk prostate cancer.
- Focused mpMRI of pelvis images will be sent to PACS for review by an independent, experienced board certified body MR radiologist without knowing clinical findings except for high risk prostate cancer.

Evaluation of imaging findings:

Reviewers review images to evaluation imaging findings without knowing clinical findings except all subjects are recently diagnosed with very high-risk or high-risk prostate cancer. Readout workflow is illustrated in Figure 2. The scores will be recorded and stored in a secured REDCap file.

Pelvic mpMRI:

1. Lesion detection and characterization utilizing PI-RADS version 2 (15).
2. Tumor staging utilizing AJCC TNM staging system (3)
3. Detection of suspicious pelvic lymph nodes.
4. Detection of suspicious osseous lesion in the pelvis.

Torso and focused C-11 choline PET/MR:

1. Lesion detection and characterization.
2. Tumor staging
3. Detection of suspicious pelvic and extrapelvic lymph nodes.
4. Detection of suspicious osseous lesion in the pelvis and extrapelvic regions.
5. Document SUV in the region of interest (ROI) if possible.

Reference standards

[figure not shown]
[figure not shown]

1. Histopathology results when available
2. Clinical imaging study (CT, bone scan, etc).
3. Clinical follow-up (progression or regression at follow-up routine clinical imaging after treatment).

Prostate tumor localization and characterization: Focused C-11 choline PET/MR and pelvic mpMRI findings to be correlated with clinical prostate biopsy and surgery results.

Lymph node metastases: Torso and focused C-11 choline PET/MR and pelvic mpMRI findings to be correlated with clinical CT, lymph node biopsy, and surgery results

Bone metastases: Torso and focused C-11 choline PET/MR and pelvic mpMRI findings to be correlated with whole body bone scan, F-18 NaF PET/CT (if available), CT, dedicated MRI, and biopsy results.

Figure 1. Illustration of Part 1 “Torso C-11 Choline PET/MR” and Part 2 “Hybrid Focused C-11 Choline PET/MR and Pelvic mpMRI.”

Acquisition time per table bed	Part 1: Torso C-11 choline PET/MR				Part 2: Hybrid dedicated focused C-11 choline PET/MR and pelvic mpMRI			
2-5 min/bed	PET		AC	Diagnostic MR pulse sequences				
2-5 min/bed	PET		AC	Diagnostic MR pulse sequences				
2-5 min/bed	PET		AC	Diagnostic MR pulse sequences				
2-5 min/bed	PET		AC	Diagnostic MR pulse sequences				
2-5 min/bed	PET		AC	Diagnostic MR pulse sequences				
2-5 min/bed	PET				Focused C-11 choline PET/MR 		Pelvic mpMRI (anatomic and functional sequences) without e-coil	
Time	25-30 min				45-50 min			

AC=attenuation correction

mpMRI = multiparametric MRI

e-coil = endorectal coil (for illustration purpose only, will not be used in current study)

* = F-18 FDG PET/MR shown for illustration purpose

** = C-11 choline PET/CT shown for illustration purpose

*** = T2W shown for illustration purpose

Figure 2. Workflow of Readout Sessions (parts 1-3)

[figure not shown]

Table 1. Summary of imaging finding evaluation

	C-11 choline PET/MR (research)	Clinical imaging exams	Reference standard	Findings
Local T staging: Prostate	Focused pelvic C-11 choline PET/MR	Pelvic mpMRI	Pathology results (biopsy, surgery if available)	Localization Characterization Local tumor (T) staging
Metastasis to pelvic lymph nodes(N)				
Pelvis	Focused C-11 choline PET/MR	Pelvic mpMRI CT	Pathology results (biopsy, surgery if available)	Localization SUV values
Torso	Torso C-11 choline PET/MR	CT	Pathology results (biopsy, surgery if available)	Localization SUV values
Metastasis to pelvic bone (M)				
Pelvis	Torso and focused C-11 choline PET/MR	Pelvic mpMRI CT Bone scan	Pathology results (biopsy, surgery if available)	Localization SUV values
Extra-pelvis	Torso C-11 choline PET/MR	CT Bone scan	Pathology results (biopsy, surgery if available)	Localization SUV values
Visceral metastasis (M)				
Visceral metastasis (M)	Torso C-11 choline PET/MR	CT	Pathology results (biopsy, surgery if available)	Localization SUV values

